- r Tanner staging assessment will be contingent on IRB/EC's approval and written informed consent from the patients' parents/legal guardian and with patient assent (as applicable). Tanner staging will be documented on the eCRF at baseline. During the study conduct, patients will have their Tanner stages documented or assessed yearly until they reach Stage 5 (see Section 4.5.8).
- s Wrist/Hand X-ray: This radiographic assessment will be contingent on IRB/EC's approval and written informed consent from the patients' parents/legal guardian and with patient assent (as applicable). One combined standard PA radiograph of the left wrist and hand will be obtained within 4 weeks of baseline and repeated yearly (± 4 weeks). If evidence of growth-plate fusion is not demonstrated at baseline but during subsequent X-rays, no further hand/wrist X-rays will be necessary provided that final growth/bone maturation has unequivocally been reached (see Section 4.5.10).
- t If a prior X-ray was obtained within the last 6 months before the WD visit, the X-ray should not be repeated.
- u "Baseline" MRI scan should be performed after the screening visit, but at least 10 days prior to the baseline visit. Baseline and Week 12 (± 2 weeks) MRI scans will be performed without a Gd-contrast agent at Week 24 (a window of minus 4 weeks can apply) and Weeks 48, 72, 96, 144, 192, 240, and 288 (window of ± 4 weeks of these scheduled visits). Also, MRI scans will be obtained in patients withdrawn from the treatment period (at a withdrawal from study visit), if not performed during the last 4 weeks.
- v Neurological examination and EDSS: See Sections 4.5.14 and 4.5.15.
- w Concomitant medications: See Section 4.4.
- x Adverse events: See Section 5.
- y Sensitive thyroid-stimulating hormone will be tested at screening and during the treatment period as indicated. Thyroid autoantibodies will be assayed only at screening.

- z Hepatitis screening and monitoring: All patients must have negative HbsAg and negative HepCAb screening test results prior to enrollment. If total HbcAb is positive at screening, HBV DNA measured by PCR must be negative to be eligible. For those patients enrolled with negative hBsAg and positive total HbcAb, HBV DNA (PCR) must be repeated every 12 weeks during the treatment period.
- aa To be completed on Visit 9 if not done at Visit 8.
- bb Immunologic assessments: Includes CD19 and other circulating B–cell subsets, T cells, and natural killer cells. On infusion visits, blood samples should be collected prior to the methylprednisolone administration.
- cc Routine safety laboratory (hematology, chemistry, and urinalysis): On infusion visits, all urine and blood samples should be collected prior to the methylprednisolone administration. At other times, samples will be collected at any time during the visit. For urinalysis, a urine dipstick for blood, protein, nitrite and glucose (using the dipsticks provided) will be performed. If abnormal and applicable a microscopic examination will be performed on site (local laboratory). For more information related to safety laboratory assessments, see Section 4.5.19.1.
- dd Serum β-hCG must be performed at screening in female patients of childbearing potential (e.g., in Tanner stages ≥ 2 or post-onset of menarche). Subsequently, urine β-hCG (sensitivity of at least 25 mIU/mL) will be performed. On infusion visits, the urine pregnancy test should be performed prior to the methylprednisolone administration in all female patients of childbearing potential. If positive, the patient will not receive the scheduled dose, and confirmation by a serum pregnancy test will be performed.
- ee Antibody titers: Measurement of antibody titers against common antigens (mumps, rubella, varicella zoster, and *S. pneumoniae*) will be performed.
- ff Plasma and urine samples for JCV will be collected at specified timepoints and analyzed in batches, if decided by the Sponsor.
-  ECG (predose and postdose): At screening, ECG may be taken at any time during the visit. On infusion visits, ECGs should be performed prior to receipt of study drug, prior to vital sign measurements and blood draws. ECG should be taken within 45 minutes prior to the methylprednisolone administration in all patients and within 60 minutes after completion of the ocrelizumab infusion (see Section 4.5.11). Additional ECGs may be taken at the discretion of the treating investigator, as required during an unscheduled visit.
- hh Vital signs (i.e., pulse rate, systolic and diastolic blood pressure, respiration rate, and temperature). On infusion visits, the vital signs should be taken within 45 minutes prior to the methylprednisolone administration in all patients. In addition, vital signs should be obtained prior to ocrelizumab infusion, then every 15 (± 5) minutes for the first hour, then every 30 (± 10) minutes until 1 hour after the end of the infusion. On non-infusion days, the vital signs may be taken at any time during the visit. Additional vital signs may be taken at the discretion of the treating investigator and should be recorded on the corresponding unscheduled Vital Signs eCRF.
- ii PK samples (predose and postdose): On infusion visits, two serum samples will be collected, one 5–30 minutes prior to the methylprednisolone administration and the second one 30 (± 10) minutes following the completion of the infusion of ocrelizumab. At other timepoints (non-infusion visits), samples will be collected at any time during the visit.
- jj ADA: On infusion visits (except on Day 15, and on the optional infusion visit for split dose if applicable), a serum sample is collected 5–30 minutes prior to the methylprednisolone administration.

Ocrelizumab—F. Hoffmann-La Roche Ltd 132/Protocol WA39085, Version 10

kk All patients will receive prophylactic treatment with an antihistamine and methylprednisolone prior to any infusion of ocrelizumab. Methylprednisolone dose (slow IV infusion to be completed approximately 30 minutes before the start of each infusion): adjusted to weight for patients < 40 kg (2 mg/kg methylprednisolone) and for patients ≥ 40 kg (100 mg methylprednisolone). In the rare case, when the use of methylprednisolone is contraindicated for the patient, an equivalent dose of an alternative steroid should be used as premedication prior to the infusion of ocrelizumab. IV or oral antihistamine (e.g., diphenhydramine) will be administered 30–60 minutes prior to ocrelizumab. The addition of an analgesic/antipyretic, such as acetaminophen/paracetamol, may also be considered.

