# 4.3.6 Criteria for Re-Treatment with Ocrelizumab

A re-evaluation of the benefit-risk of continuing study treatment by the treating investigator must be performed for each patient at the end of the first 24 weeks and prior to any further dosing, and therapy continuation will only be granted to those patients where the benefit-risk is considered to be favorable.

A visit within 2 weeks prior to any dosing visit (i.e., scheduled dosing visit or delayed dosing visit) will be required to collect blood samples and patient information to enable the treating investigator to assess whether a patient meets re-treatment criteria at the time of an infusion with study drug.

Treating investigator must ensure he or she has reviewed the laboratory results of the patient prior to re-treatment with ocrelizumab. Any repeat laboratory tests must be performed, analyzed, and reviewed before administration of ocrelizumab.

Prior to re-treatment, the following conditions must be met:

- Absence of life-threatening (Grade 4) infusion-related event that occurred during a previous ocrelizumab infusion
- Absence of severe allergic or anaphylactic reaction to an ocrelizumab infusion
- Absence of active infection regardless of the grade (including active tuberculosis [TB] infection, either new onset or reactivation) and treatment with any anti-infective medications has been completed (see Section 5.1.1.2)

A patient with active TB infection or a Grade 3 infection must suspend ocrelizumab treatment for as long as needed to ensure full resolution of the infection.

The patient should receive medical care in adherence with local/national requirements until complete resolution of the infection and should be monitored subsequently as per local medical plans. Upon resolution of the infection and based on individual benefit-risk assessments, the patient will have the opportunity to restart ocrelizumab treatment if it is considered beneficial for him or her. Otherwise, the treating investigator can decide to permanently stop ocrelizumab.

- Absence of any significant or uncontrolled medical condition or treatment-emergent, clinically significant, laboratory abnormality
- ANC  $\geq 1.5 \times 10^{3}/\mu L$
- CD4 levels:
  - For children and adolescents: percent CD4  $\geq$  25%
  - For patients  $\geq$  18 years of age, the adult reference applies: CD4 cell count  $\geq$  250/ $\mu L$
- IgG Level:
  - For children and adolescents:  $IgG \ge 4.6 g/L$

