#### Appendix 1 Schedule of Activities

#### Table 1 Schedule of Activities for Dose Exploration Period

	Screening a (MN) a		Do	se Expl	oration	Period (	24 Wee	eks)		⁄isit h	i,i O	Ĺ	sit k
Site or optional MN visit c	1	2	3	4	5	6	7 b	8 (MN) opt. d	9 e, f	V guiso	sit for SI	Site/MN	Irtmt Vi
Week	-8 to-1	1	2	4	8	12	16	22 g	24	рő	ſ<ïs	ed.	Ē
Study day (±days)	_56 to _1	1	15 (±3)	29 (±4)	57 (±4)	85 (±4)	113 (±4)	155 (±6)	169 (±6)	Delaye	Opt In	Unsch	WD fro
Telephone interview (±6 days) 							Wee	ek 20					
Informed consent and assent m	х												
Demographic data	Х												
Medical history and baseline conditions	х	Х											
Review of eligibility criteria	x	х											
SDMT		х							Х	(X)		(X)	x
Visual testing (ETDRS and LCVA charts) n		Х							Х	(X)		(X)	x
Physical examination o	X	Х	х	Х	Х	х	х	X	Х	Х	Х	X	x
Weight p	X	Х							Х	(X)			x
Height q		х							Х	(X)			x
Tanner staging r		X								(X)			x
Date of menarche		х	х	х	х	х	х	Х	Х	(X)			x
Wrist/Hand X–ray s	X s									(X)			(x) t
Brain MRI scan u	x					x			Х	(X)		X	x
Neurological examination and EDSS v	X	х				х			Х	(X)		X	x
Concomitant medication w		Х	X	х	х	X	x	X	X	Х	Х	X	X
Adverse events x	only SAEs	Х	X	Х	Х	X	X	X	X	Х	Х	X	X
Clinical relapses			х	Х	X	X	X	x	х	х	х	X	X

A	pendix	1:	Schedule	of	Activities
---	--------	----	----------	----	------------

	Screening a (MN) a		Do	se Expl	oration	Period (	(24 Wee	eks)		ʻisit h	i,h C	i	sit k
Site or optional MN visit c	1	2	3	4	5	6	7 b	8 (MN) opt. d	9 e, f	osing V	it for SI	Site/MN	Irtmt Vis
Week	-8 to-1	1	2	4	8	12	16	22 g	24	D P	Vis	ed.	E E
Study day (±days)	_ 56 to _1	1	15 (±3)	29 (±4)	57 (±4)	85 (±4)	113 (±4)	155 (±6)	169 (±6)	Delaye	Opt Inf	Unsch	WD fro
Thyroid function tests y	X (MN)								x	(x)		(x)	x
Hepatitis screening z	X (MN)												
Hepatitis B Virus DNA z	X (MN)	(X)			(X)				(X)			(X)	(X)
Rapid plasma reagin	X (MN)												
CD4 percentage	X (MN)							X				(X)	
Total Ig, IgA, IgG, and IgM	X (MN)	Х				X		X	x aa	(X)		(X)	X

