Immunologic assessments (including CD4%) bb		Х	X	Х	х	X	X		Х	(X)		(X)	X
Routine safety laboratory cc	X (MN)	х	x			x		X	x aa	(X)		(X)	x
Pregnancy test dd	X (MN)	х	х			X		X	Х	Х	х	(X)	x
Antibody titers ee		Х				X			X	(X)		(X)	x
Plasma/Urine banking for JCV ff		х							X	(X)		(X)	X
Review of re-treatment criteria g			х						X	X	Х		
Twelve-lead ECG (predose and postdose) gg	X	х	x						X	x	x	X	x
Vital signs hh	X	Х	X	Х	X	X	X	X	Х	X	х	X	x
PK samples (predose and postdose) ii		х	X	х	Х	X	X		X	X	Х		x
ADA jj		х							х	X			x
Pre-medications kk		х	Х						X	X	X		
Ocrelizumab administration g, i, l		Х	x						x	x	x		

ADA = anti-drug antibody; AE = adverse event;  $\beta$ -hCG = beta-human chorionic growth hormone; EC = Ethics Committee; eCRF = electronic case report form; EDSS = Expanded Disability Status Scale; ETDRS = Early Treatment Diabetic Retinopathy Study; Gd = gadolinium; HbcAb = hepatitis B core antigen; HbsAg = hepatitis B surface antigen; HBV = hepatitis B virus; HepCAb = hepatitis C antibody; Ig = immunoglobulin; IMC = Internal Monitoring Committee; Inf. = infusion; IRB = Institutional Review Board; IRR = infusion-related reaction; JCV = JC-virus; LCVA = low-contrast visual acuity; LLN = lower limit of normal; MN = mobile nursing; MRI = magnetic resonance imaging; opt = optional; PA = posteroanterior; PCR = polymerase chain reaction; PK = pharmacokinetic; SAE = serious adverse event; SD = split dose; SDMT = Symbol Digit Modalities Test; SFU = safety follow-up period; Trtmt = treatment; Unsched = unscheduled; WD = withdrawal.

Notes:

Marks in parentheses are optional and may be done as appropriate (e.g., if not done at the scheduled dosing visit or if needs to be repeated).

Columns shaded in gray indicate visits that include an ocrelizumab infusion.

(MN) indicates that this visit may be performed as a mobile nursing visit. Note for the screening visit: For the patient's convenience, the mobile nursing service can be requested if any laboratory tests have to be repeated.

For consistency, it is recommended the same examiner will perform the same assessment at each visit using the same instrument in the same patient.

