- d Visit 8 (site or optional MN visit, as applicable) at Week 22 is only to be scheduled for patients entering the optional ocrelizumab extension period (footnote b). Assessments performed at this visit will serve to determine if patients meet criteria for re-treatment with ocrelizumab (footnote g) before the next optional infusion of ocrelizumab at Week 24 (Visit 9) (footnote f).
- Visit 9 at Week 24 is mandatory for all patients who received the first dose of ocrelizumab. For patients continuing the study in the optional ocrelizumab extension period (footnote b), the second dose of ocrelizumab will be administered if all re-treatment criteria are met (footnote g) and all assessments described for Visit 9 will be performed.

Patients who are not continuing the study in the optional ocrelizumab extension period will not receive further treatment with ocrelizumab, assessments corresponding to withdrawal from treatment visit will apply, and these patients will enter the SFU period (see Section 3.1.1.4 and 4.5.3.6).

- f At Week 24 (Visit 9), only patients continuing in the optional ocrelizumab extension period (footnote b) will receive an infusion of ocrelizumab with either the dose (e.g., 300 mg or 600 mg) initially assigned to them or with the dose selected by the IMC for the subsequent Phase III study in children/adolescents, as applicable. In a situation where the second dose of ocrelizumab is higher than the initial treatment regimen, that dose must be administered as two infusions of half the dose 14 days apart to mitigate the risk and severity of IRRs. In this case, the second infusion will take place as an optional infusion visit for split dose. The benefits and risks of continuing study treatment should be discussed by the treating investigator with the parents/legal guardian and patient in advance, and prior to any further dosing. In situations where patients cannot receive their second dose within 24 hours of the Week 24 visit, they should be re-scheduled for a delayed dosing visit (footnotes g and h).

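### The HBV DNA rows in Tables 1 and 2b mark gaps of up to 16 and 26 weeks, although their own footnotes require testing every 12 weeks on treatment

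*Combined protocol and SAP*

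**What the plan says.** Section 4.5.19.4 of the protocol admits patients with past, resolved hepatitis B (total HBcAb positive, viral DNA negative) and has their viral DNA followed. It gives no interval and points to the schedule of activities in Appendix 1. There, footnote z to Table 1 and footnote u to Table 2b say the same thing for these patients: "HBV DNA (PCR) must be repeated every 12 weeks during the treatment period".

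The rows that carry the footnotes read as follows.

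- Table 1, row "Hepatitis B Virus DNA z": marked at screening and at Weeks 1, 8 and 24; blank at Weeks 2, 4, 12, 16 and 22.
- Table 2b, the corresponding row: marked at Weeks 190, 214, 238, 262 and 288; blank at Weeks 204, 228, 252 and 276 and on the infusion days.

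Every on-treatment mark in both rows is in parentheses, and the notes under both tables say that such marks are optional.

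On checks before dosing, Section 4.3.6 calls for a blood-sample visit ("A visit within 2 weeks prior to any dosing visit") and adds: "Treating investigator must ensure he or she has reviewed the laboratory results of the patient prior to re-treatment with ocrelizumab". For Dose 2 that visit is Week 22, and footnote d to Table 1 states its purpose: "Assessments performed at this visit will serve to determine if patients meet criteria for re-treatment with ocrelizumab". The rows "Total Ig, IgA, IgG, and IgM" and "Routine safety laboratory cc" are marked at Week 22, with Week 24 as the fallback under footnote aa ("To be completed on Visit 9" when Visit 8 missed them). The HBV DNA row is blank at Week 22 and marked on the Week 24 infusion day.

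**The concern.** One table gives two instructions for the same safety test, and the body text does not choose between them. Under Section 4.5.19.4 a confirmed positive HBV DNA ends further infusions, and under Section 4.6.1 active hepatitis B, including reactivation, requires permanent discontinuation. Section 5.1.1.2 records one reactivation in an ocrelizumab-treated patient with rheumatoid arthritis, and none in interventional MS studies. If visits are planned from the grid, a reactivation could be found later than the footnote intends.

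Table 3 suggests that the grid is the part in error. After treatment stops, it marks HBV DNA at each 12-weekly follow-up visit, and its footnote f limits the test to this same subset. On the Table 2b grid, patients are tested about half as often on drug as they are afterwards.

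**Working it through.** **Inputs.** Required interval: 12 weeks = 84 days (footnotes z and u). Study days and visit windows come from the header rows of Tables 1 and 2b. Gap = difference in study days; weeks = days / 7.

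| Table | Marked weeks | Days | Weeks |
|---|---|---|---|
| 1 | 1 to 8 | 57 − 1 = 56 | 8 |
| 1 | 8 to 24 | 169 − 57 = 112 | 16 |
| 2b | 190 to 214 | 1499 − 1331 = 168 | 24 |
| 2b | 214 to 238 | 1667 − 1499 = 168 | 24 |
| 2b | 238 to 262 | 1835 − 1667 = 168 | 24 |
| 2b | 262 to 288 | 2017 − 1835 = 182 | 26 |

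**Can visit windows close the gaps?** Week 8 has ±4 days and Week 24 has ±6, so the Table 1 gap lies between 112 − 10 = 102 days (14.6 weeks) and 112 + 10 = 122 days (17.4 weeks). In Table 2b each visit has ±6 days, so the shortest possible gap is 168 − 12 = 156 days (22.3 weeks). None reaches 84 days.

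**Number of tests.** Table 2b spans 2017 − 1331 = 686 days = 98 weeks. 98 / 12 = 8.2 intervals, or about 9 test points; the row marks 5.

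**Reading of the rows.** The Table 1 row has 13 cells for 13 columns and the Table 2b row 17 for 17, and the rows next to it in Table 1 line up. The Table 2a row is broken in the text available here, so nothing is claimed about it.

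**Latest earlier mark before each infusion.** Week 24: Week 8, 16 weeks before. Weeks 192, 216, 240 and 264: Weeks 190, 214, 238 and 262, two weeks before each.

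**With the added marks.**

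- Table 1: Day 1 to Day 85 (Week 12) is 84 days, 12 weeks. Day 85 to Day 169 (Week 24) is 84 days, 12 weeks; to Day 155 (Week 22) it is 70 days, 10 weeks.
- Table 2b (Weeks 190, 204, 214, 228, 238, 252, 262, 276, 288): 14, 10, 14, 10, 14, 10, 14 and 12 weeks.

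A tolerance of ±2 weeks on the interval would have no slack. With ±6-day windows a nominal 98 days can become 98 + 12 = 110 days (15.7 weeks), and a nominal 70 days can become 70 − 12 = 58 days (8.3 weeks).

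**The case against.** The strongest reply is that the rule already exists and prevails. The footnote is mandatory and attached to the row label, while the marks are optional by the tables' own definition. The schedule to which Section 4.5.19.4 refers includes its footnotes, and unscheduled safety samples are allowed at any time. Section 5.1.1.2 also sends seropositive patients to liver disease experts before treatment and has them monitored to local standards. Chemistry, including ALT and AST, is drawn at Weeks 12 and 22, and Section 4.5.19.4 withholds drug while viral hepatitis is being excluded.

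Most of this stands. It shows that a careful site can comply and that there are other safeguards. It does not make the grid agree with the footnote.

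Three stronger readings are tempting, and the documents do not support them.

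- *HBcAb-positive patients go unmonitored on treatment.* They do not: the footnotes require the test and the grid still marks some of it.
- *The blank at Week 22 breaches the protocol.* No section requires HBV DNA at that visit, and it is not named among the Section 4.3.6 criteria. A site following footnote z would hold a result from about Week 12. The 16-week-old result before Dose 2 arises only if the grid alone is followed and the infusion-day sample is not reported in time; no turnaround time is given.
- *Later doses are given without a recent result.* Table 2b marks a sample two weeks before each infusion, so the effect there is later detection between doses.

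A cell count alone cannot exclude a mark displaced by one column, so the Table 1 row also deserves a look in the source PDF, although nothing suggests displacement.

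**Conclusion.** The inconsistency is real and should be corrected. Against a required 12 weeks, the grid allows 16 weeks in Table 1 and 24 to 26 weeks in Table 2b. It is a conflict between a footnote and its own row, not an absence of monitoring.

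Its reach is small. It concerns only patients enrolled HBsAg-negative, HBcAb-positive and HBV DNA-negative. Their number is not stated and may be zero, in a study of at most about 36. Recruitment at 40 kg and above is closed (Section 4.2), so the Dose 2 timing matters mainly for any further enrolment below 40 kg. No endpoint or analysis depends on it. The conclusion assumes that the two rows are printed as they read here.

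**What to change.** 1. Mark HBV DNA at Week 12 in Table 1 and at Weeks 204, 228, 252 and 276 in Table 2b. Blood is already drawn at all five visits. Keep the existing pre-infusion marks and Week 288; the Week 8 mark can stay.
2. Check the Table 2a row in the source PDF and align it in the same way.
3. State that parentheses in this row mean required in HBcAb-positive patients, in line with footnote f to Table 3.
4. Reword footnotes z and u to *approximately every 12 weeks, at the visits marked, within the visit windows*, and do not use a ±2-week tolerance.
5. As a secondary improvement, not the correction of a breach, draw the pre-Dose 2 sample at Week 22, or at Week 24 if Visit 8 missed it, as footnote aa already does for other tests. The result can then be reviewed before dosing, as Table 2b allows for its infusions.

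The cost is row and footnote edits plus up to 1 + 4 = 5 PCRs beyond the grid of Tables 1 and 2b for each affected patient who completes Week 288. Week 22 replaces Week 24 and adds none. Most of the five are already required by the footnotes. Any Table 2a tests are not counted. The PCR sample volume is not stated and must fit the blood-volume limits in Section 4.5.19.

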Appendix 1: Schedule of Activitie
-----------------------------------

						C	ptiona	al Ocre	lizuma	b Exte	ension	(264 V	Veeks)	а						sit d	d, e		6
Site or optional MN visit b	10 (MN)	11 (MN)	12	13 (MN)	14 (MN)	15	16 (MN)	17 (MN)	18	19 (MN)	20 (MN)	21	22 (MN)	23 (MN)	24	25 (MN)	26 (MN)	27	28 (MN)	sing Vis	for SD	ite/MN f	tmt Visit
Week	36	46 c	48	60	70 c	72	84	94 c	96	108	118 c	120	132	142 c	144	156	166 c	168	180	۱å	Visit	d. S	Ъ
Study day (±days)	253 (±6)	323 (±6)	337 (±6)	421 (±6)	491 (±6)	505 (±6)	589 (±6)	659 (±6)	673 (±6)	757 (±6)	827 (±6)	841 (±6)	925 (±6)	995 (±6)	1009 (±6)	1093 (±6)	1163 (±6)	1177 (±6)	1261 (±6)	Delayed	Opt Inf \	Unsche	WD fron
Telephone interview h	At V	Veeks	28, 32	, 40, 4	4, 52,	56, 64	, 68, 7	6, 80,	88, 92 172, 1	, 100, 76 (± 6	104, 1 5 days)	12, 11 )	6, 124	, 128,	136, 1	40, 14	8, 152,	, 160,	164,				
SDMT			х			х			х			х			х			x		(X)		(X)	x
Visual testing (ETDRS and LCVA charts) i			x			x			x			x			x			x		(x)		(X)	x
Physical examination j	х	х	х	x	х	х	х	х	х	х	X	х	х	х	х	x	х	x	x	x	x	x	x
Weight k			х			х			х			х			X			x		(X)			x
Height 			х			x			х			х			х			x		(X)			x
Tanner staging m			х						х						х					(X)			x
Date of menarche	X	X	Х	x	Х	X	х	х	Х	х	x	Х	х	Х	Х	x	x	X	х	(X)			x
Wrist/Hand X–ray n			Х						Х						Х					(X)			(X) °
Brain MRI scan p			Х			X			Х						X					(X)		X	X
Neurological examination and EDSS q			x			x			x			x			x			x		(x)		x	x
Concomitant medication r	x	x	x	x	x	x	x	x	x	x	x	x	x	x	x	x	x	x	x	x	x	x	x
Adverse events s	х	х	х	X	х	X	х	х	х	х	X	х	х	х	х	X	X	x	X	x	x	x	x
Clinical relapses	X	X	X	X	X	X	X	Х	х	X	X	x	X	X	X	X	X	x	X	x	x	x	X

A	p	pendix	1:	Schedule o	of Activities
---	---	--------	----	------------	---------------

						C	ptiona	l Ocre	lizuma	b Exte	nsion	(264 V	Veeks)	а						sit d	d, e		f a
Site or optional MN visit b	10 (MN)	11 (MN)	12	13 (MN)	14 (MN)	15	16 (MN)	17 (MN)	18	19 (MN)	20 (MN)	21	22 (MN)	23 (MN)	24	25 (MN)	26 (MN)	27	28 (MN)	sing Vis	for SD	ite/MN f	tmt Visit
Week	36	46 c	48	60	70 c	72	84	94 c	96	108	118 c	120	132	142 c	144	156	166 c	168	180	Ď	/isit	d. S	n Tr
Study day ( $\pm$ days)	253 (±6)	323 (±6)	337 (±6)	421 (±6)	491 (±6)	505 (±6)	589 (±6)	659 (±6)	673 (±6)	757 (±6)	827 (±6)	841 (±6)	925 (±6)	995 (±6)	1009 (±6)	1093 (±6)	1163 (±6)	1177 (±6)	1261 (±6)	Delayed	Opt Inf \	Unsche	WD fron
Thyroid function tests t			x			x			x			x			x			x		(x)		(x)	x
Hepatitis B ∨irus DNA u		(X)			(X)					(X)	(x)												
Total Ig, IgA, IgG, and IgM		x			x			x			x			x			x			(x)		(x)	x
Immunologic assessments (including CD4%) v	x	x		x	x		x	x		x	x		x	x		x	x		x	(x)		(x)	x
Routine safety laboratory w	x	x	(x)	x	x	(X)	x	(x)		(x)	x												
Pregnancy test ×	х	х	х	X	X	Х	X	x	X	x	х	X	X	X	х	X	X	X	х	x	х	(X)	Х
Antibody titers y			х			х			X			X			х			x		(X)		(X)	X
Plasma/Urine banking for JCV z			x			x			x			x			x			x		(x)		(x)	x
Review of re- treatment criteria c			x			x			x			x			x			x		x	x		
Twelve-lead ECG (predose and postdose) aa			x			x			x			x			x			x		x	x	x	x
Vital signs bb	Х	X	X	X	X	X	X	X	X	X	Х	X	X	X	X	X	X	X	Х	х	х	Х	х

Ocrelizumab—F. Hoffmann-La Roche Ltd 135/Protocol WA39085, Version 10

